- If eligible based on S0 data, participants will undergo baseline bronchoscopy with bronchoalveolar lavage (BAL) for collection of lung cathelicidin levels (visit B1). Blood for cathelicidin, vitamin D binding protein, vitamin D and PBMC will be collected at this visit.
- They will then return to the Meadowmont research clinic weekly for eight weeks of directly observed vitamin D supplementation as well as assessment of adverse events (visits V0-V7).
 - After the initial four weeks of treatment (V4), all patients will be evaluated and have blood work obtained for calcium level to monitor for hypercalcemia.
 - Patients will be screened at each weekly visit for symptoms of hypercalcemia.
- After 8 weeks of vitamin D treatment, serum 25OH-VitD levels will be measured (visit V8) to ensure increased level prior to undergoing bronchoscopy. Individuals not increasing vitamin D > 20 after 8 weeks will not be eligible for B2 bronchoscopy and will be deemed to have completed study. Blood for BMP/ calcium level will also be collected.
- A second BAL collection will occur after the eight week of vitamin D treatment to measure cathelicidin in the plasma and the BAL (visit B2). Blood for cathelicidin, vitamin D binding protein, vitamin D and PBMC will also be collected at this visit.
- A 24 hour post-bronchoscopy follow-up phone call will occur after B1 and B2
- All procedures will be research related. A visit window of ± 1 day is acceptable for all study visits except B1 and B2, where a 28 day window is permissible given potential delay in laboratory results and bronchoscopy scheduling.

Table. Study Data Collection Schedule

Visit	S0	B1	V0	V1	V2	V3	V4	V5	V6	V7	V8	B2
Time (weeks)	-2	-1	0	1	2	3	4	5	6	7	8	9
Window (+/- days)	0	28	1	1	1	1	1	1	1	1	1	28
Visit Duration (hrs)	2	5	1	0.5	0.5	0.5	1	0.5	0.5	0.5	1	5
Informed Consent	•											
Spirometry	•											
Vitamin D	•						•				•	
Vit D binding prot/cathelicidin	•										•	

PBMC		•									•
BMP/ calcium	•						•			•	
BAL		•									•
Drug administration			•	•	•	•	•	•	•	•	
Adverse events & interval history				•	•	•	•	•	•	•	

Key: Time= nominal visit time; S=screening visit, Bn= Bronchoscopy visit n, Vn=Study visit

SECTION 2: RECRUITMENT

2.1 Definition of Recruitment & Consent: Recruitment is establishing eligibility of the potential candidate and informing the candidate of their eligibility and signing of the informed consent form by the potential candidate.

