3.2 Screening Visit (S0)

- i. Review/sign consent form
- ii. Assignment of study ID
 - a. Using “VitDXXX” where
XXX= sequential numbers from 501-999
- iii. Completion of **demographics form**
- iv. Urine pregnancy test (for women of childbearing age)
- v. Performance of pre- and post-bronchodilator spirometry (4 puffs albuterol)
- vi. Completion of **screening form** to determine eligibility
- vii. If eligibility confirmed, obtain blood testing for screening visit (see **laboratory processing section**)
 - a. One-3.5 ml SST to UNC McLendon Lab for eligibility screening
 - i. Serum 25OH-Vitamin D
 - ii. Serum Basic metabolic panel
 - b. One 8.5 ml SST for serum storage
 - i. Serum for 25OH-Vitamin D and vitamin D binding protein
 - c. Two 4 ml EDTA Lavender for plasma storage
 - i. Plasma for cathelicidin
- viii. Confirm contact number to reach participant after 25OH-VitD and BMP resulted.
- ix. Payment to participant
- x. After labs resulted, PI to review vitamin D/BMP results and determine eligibility
- xi. MD to contact person to arrange bronchoscopy

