3.3 Bronchoscopy (B1)

- i. Before scheduling the first of the two bronchoscopy procedures, it should be established that
 - i. Patient has signed IRB-approved consent for the research protocol
 - ii. Has met the inclusion criteria for the study.
 - iii. The benefits and risks of the procedure have been explained to the participant and patient has given consent for the procedure.
- ii. The target windows for scheduling the bronchoscopy is 28 days after S0 visit for the first procedure and 1 week after V8 for the second procedure.

- iii. Day of bronchoscopy, the following bloods will be collected (processed at [name] lab):
 - a. Two 10 ml Green Top Lithium tubes for PBMC storage

See “**BRONCHOSCOPY PROCEDURES**” for bronchoscopy procedure details

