The following pages include a separate page for each study visit with a checklist of items that must be completed at each visit. These pages should be printed and used as a step-by-step guide of each visit.

Assigned ID: VitD _____	Participant Initials: _____	Date: _____
-------------------------	-----------------------------	-------------

S0- Screening Visit Checklist

- Review and sign consent form
- Assign study ID
- Complete demographics form
- Urine pregnancy test (for women of childbearing age)
- Pre- and post-bronchodilator spirometry
- Complete screening form
- If eligibility confirmed, obtain blood testing
 - One 3.5 ml SST to UNC McLendon Lab for eligibility screening
(BMP, 25-OH vitamin D)
 - One 8.5 ml SST for serum storage (25-OH vitamin D, vitamin D binding protein)
 - Two 4 ml EDTA lavender tube for plasma storage (cathelicidin)
- Confirm contact phone number
- Provide participant with “Bronchoscopy Handout”
- Payment to participant:
- Notify MD of blood results for review and scheduling of bronchoscopy

Review total recruitment:

Eligibility: 25OH VitD <20ng/ml (with targeted recruitment of at least 10 participants with level <10 ng/ml)

Bronchoscopy scheduling: Target 1 week ± 28 days

- Once bronchoscopy is scheduled, V0 should be scheduled within 1 week ±1 day of bronchoscopy)
- Notify pharmacy of medication pickup

Assigned ID: VitD _____

Participant Initials: _____

Date: _____

B1- Bronchoscopy #1 Visit Checklist

- Review consent form for completion
- Obtain blood testing
 - Two 10 ml Green Top Lithium tubes for PBMC storage
- Review labs to confirm vitamin D <20 ng/ml
- Escort patient to bronchoscopy
- Payment to participant:
- MD to complete bronchoscopy form
- Staff to complete bronchoscopy sample processing form
- Confirm V0 is scheduled (within 1 week \pm 1 day of bronchoscopy)

Assigned ID: VitD _____ Participant Initials: _____ Date: _____

V0- Initial medication administration checklist

- Go to pharmacy
- Provide participant one pill of 50,000 IU vitamin D to take with water at visit
- Provide participant informational flyer regarding vitamin D side effects
- Complete Vitamin D Subject Specific Accountability Record
- Schedule V1 in 7±1 days
- Payment to participant:

Assigned ID: VitD _____	Participant Initials: _____	Date: _____
--------------------------------	------------------------------------	--------------------

V1- Follow-up visit checklist

- Go to pharmacy
- Complete adverse events form

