		Bal Cells	cells	Depends on Bal Cell count	10x10 ⁶ Bal Cells/ 1.0mL	minus 80° overnight to minus 140°
Green top tube	20 ml	PBMC	PBMC	Depends on PBMC count	10x10 ⁶ PBMC/ 1.0mL	minus 80° overnight to minus 140°
Lavender top EDTA tube for plasma	10 ml	Plasma (250 microliter aliquots)	Plasma	As many as possible	250 microlit	minus 80 °
SST top for serum	8 ml	Serum (250 microliter aliquots)	Serum	As many as possible	250 microlit	minus 80 °

SECTION 8: BRONCHOSCOPY PROCEDURES

- i. Patient preparation**
 - a. The participant should be interviewed prior to the procedure to ensure that there are no contraindications to performing the bronchoscopy such as
 - i. recent acute or serious illness
 - ii. anticoagulation or bleeding disorder
 - iii. fever
 - iv. oxygen desaturation on room air
 - v. allergy to local anesthetics or sedation
 - vi. food intake within 6 hours.
 - b. Patients should be instructed to take their usual morning oral medications with a small sip of water.
 - c. Patients should also have a companion or reliable escorted means of transportation home after the procedure so that they can safely return home after the procedure.
 - d. The patient should be informed that the procedure is being performed for research purposes and is not for clinical care.
 - e. The details of the procedure should be explained to the participant and consent obtained in accordance with local hospital or clinic practices and procedures.
 - f. Risks related to the procedure:
 - i. allergic or adverse reaction to sedation or local anesthesia
 - ii. nose-bleed
 - iii. sore-throat
 - iv. coughing
 - v. chest soreness from coughing
 - vi. fever
 - vii. infection
 - g. Participant will be reimbursed in the form of a check, given to participant immediately prior to procedure

- ii. Conduct of the procedure**

- a. Sedation**
 - i. Before sedation, a “time-out” should be performed to verify that the patient is correctly identified and is undergoing a bronchoscopy.
 - ii. The bronchoscopy insertion orifice should be ascertained (right or left nostril or mouth) and local anesthetic applied in accordance with local practice.
 - iii. The patient is moderately sedated during monitoring of vital signs and oxygenation according to local procedures.
 - iv. Typically a benzodiazepine (e.g midazolam) and a narcotic (e.g. fentanyl) are used.

1. Upper limits of sedation
 - a. Fentanyl 400 mcg IV
 - b. Versed 6 mg IV

b. Method

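### The only pregnancy test listed is at screening (S0), with none before either bronchoscopy or the first dose; UNC's B1 lab review also cannot show vitamin D started since S0

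*Protocol*

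**What the plan says.** **Pregnancy.** Section 2.4 of both site protocols excludes pregnant women, requires a negative test without saying when, and asks for two contraceptive methods throughout the study. Section 3.2 and the S0 checklist at each site list "Urine pregnancy test (for women of childbearing age)". The section 3 steps and Section 5 checklists for B1, V0 to V8 and B2 list no further test.

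**Timing.** The UNC S0 checklist puts B1 one week after S0, plus or minus 28 days. UNC section 3.3 differs: "The target windows for scheduling the bronchoscopy is 28 days after S0 visit for the first procedure". The Bayview S0 checklist allows one week plus or minus 5 days, while its schedule table gives B1 a 28-day window. V0 follows B1 by a week, give or take a day.

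**Controls before bronchoscopy.** Section 3.3 requires staff to establish, before scheduling, that the patient "Has met the inclusion criteria for the study". Section 3.2 has "MD to contact person to arrange bronchoscopy", with no questions specified. Section 8 (Patient preparation) requires an interview for contraindications, with six examples introduced as an open list, and "consent obtained in accordance with local hospital or clinic practices and procedures".

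**Vitamin D.** Current supplement use is an exclusion. The UNC B1 checklist says "Review labs to confirm vitamin D <20 ng/ml". The B1 blood in UNC section 3.3 and in that checklist is "Two 10 ml Green Top Lithium tubes for PBMC storage" only. UNC section 1.4 says otherwise of B1: "Blood for cathelicidin, vitamin D binding protein, vitamin D and PBMC will be collected at this visit". The interval-history row of the schedule starts at V1, after the first dose.

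**The concern.** Pregnancy status can change after screening, and the contraception requirement shows that the plan treats it as a continuing matter. Yet no listed step verifies it on the day of either sedation or before the first 50,000 IU dose. Followed as written, the procedures allow a woman to reach these points on a result several weeks old.

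The vitamin D part concerns the primary outcome. The B1 lavage is the pre-supplementation value in a single-arm paired comparison. A participant invited to bronchoscopy has a level below 20 ng/ml and might start an over-the-counter product before B1. No listed B1 or V0 step asks about this. At UNC the lab line on the B1 checklist could be taken for a fresh check when it is not one. The SAP's only analysis set takes everyone with consent and a baseline bronchoscopy, so it has no rule that would set such a pair aside.

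**Working it through.** The plan states no figure for the age of the pregnancy result, so there is none to reproduce. The intervals follow from its schedules.

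**Inputs**
- Nominal weeks (schedule table, both sites): S0 = -2, B1 = -1, V0 = 0, V8 = 8, B2 = 9.
- Windows (same table): 28 days for B1 and B2, 1 day for V0 to V8.
- S0 to B1: 7 ± 28 days (UNC checklist), 28 days (UNC section 3.3), 7 ± 5 days (Bayview checklist).
- B1 to V0: 7 ± 1 days (checklists, both sites).
- V0 to V8: eight intervals of 7 ± 1 days (checklists).
- V8 to B2: nominally 7 days, ± 28 in the table and ± 5 in the V8 checklist.

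**Days since the S0 test, at B1 and at V0**

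| Route | B1 | V0 |
|---|---|---|
| Nominal, both sites | 7 | 14 |
| UNC checklist, longest | 7 + 28 = 35 | 35 + 8 = 43 |
| UNC section 3.3 target | 28 | up to 28 + 8 = 36 |
| Bayview checklist, longest | 7 + 5 = 12 | 12 + 8 = 20 |
| Bayview table window, longest | 7 + 28 = 35 | 35 + 8 = 43 |

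Adding a 28-day window to the section 3.3 target would give 56 and 64 days. I do not rely on that reading.

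**Days since the S0 test, at B2**
- Nominal: week -2 to week 9 is 11 × 7 = 77.
- Longest by the schedule table: 77 + 28 = 105.
- UNC windows chained, with the 28-day B2 window: 35 + 8 + (8 × 8 = 64) + (7 + 28 = 35) = 142.
- The same chain with the V8 checklist's ± 5 days: 35 + 8 + 64 + (7 + 5 = 12) = 119.

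**Age of a B1 retest at the first dose:** 7 ± 1, so 6 to 8 days.

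**What the UNC B1 lab line can show.** The UNC schedule and visit steps draw vitamin D blood at S0, V4 and V8. At B1 they draw PBMC tubes only, so the one result on file is from S0. If section 1.4 governs and a sample is also taken at B1, a change could be found later. It could hardly be found before that day's lavage, because section 3.2 treats 25-OH vitamin D as a result returned after the visit. The supplied Bayview text stores B1 serum for 25-OH vitamin D, so later detection is possible there. The undetected-start issue is therefore mainly UNC's.

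**Direction of any effect.** Section 1.2 hypothesizes that supplementation raises lung cathelicidin. If so, vitamin D taken before B1 raises the baseline and makes the before-after difference smaller. The documents give no rate of self-started use, no dose and no effect size, so the amount cannot be computed.

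**The case against.** The strongest reply is that controls already exist. Section 8's interview takes place before the bronchoscopy and its list of contraindications is open, so pregnancy could be asked about before B1 and before B2. Local consent and sedation practice may include a pregnancy test. Two contraceptive methods are required. This lowers the risk, and a reader who inferred that nothing stands between an old result and sedation would be going too far. But none of the six named contraindications is pregnancy or supplement use, and an interview is not a test. The scheduling condition covers inclusion criteria only, and the S0 result satisfies it.

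The second reply is that the supplied text is incomplete. The consent pages, the Section 6 forms, the bronchoscopy form, the telephone script and the handouts cannot be seen. Any of them may already ask about vitamin D or tell participants not to start it. This stands, and it is why the supplement part is secondary and conditional. The supplied Bayview text is version 1.7 of April 2016, whereas the SAP cites a COPD protocol dated 8/23/17, so statements about Bayview apply only to the supplied text.

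Third, a reader might infer that UNC's B1 lab line is an error. It is not. Inclusion vi is defined at screening, and re-reading the S0 value is a valid file check of it. The limit is only that it cannot show a later change.

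**Conclusion.** The point holds as a minor one. In the procedures supplied for both sites, the pregnancy result is nominally 7 days old at B1, 14 at the first dose and 77 at B2. The windows permit 35, 43 and, depending on how they are read, 105 to 142. A gap of five to six weeks before the first dose is the limit of the windows and not the expected case, although UNC section 3.3 makes four weeks to B1 the target.

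Three stronger readings are not supported:
- That the timing problem is confined to UNC. Bayview's checklist is tighter, but its table window allows the same 35 and 43 days.
- That the primary result is materially biased. Only the direction can be stated, toward a smaller change, and it depends on the trial's own hypothesis.
- That UNC's plasma baseline is certainly untouched. Section 3.2 draws it at S0, which would protect it, but section 1.4 also places cathelicidin blood at B1.

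The conclusion assumes that staff follow the listed steps and that the unseen forms and local practice add nothing further.

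**What to change.** 1. **Main change, both sites.** Repeat the urine pregnancy test for women of childbearing age on the day of B1, before sedation, and again before B2. Add it to section 3 and to the B1 and B2 checklists. The B1 result also serves the first dose, which follows 6 to 8 days later.
2. **Secondary change, unless the consent, handouts or Section 6 forms already cover it.** Tell participants at S0 not to start non-study vitamin D. Reword UNC's B1 line to: *confirm S0 25-OH vitamin D <20 ng/ml and no vitamin D started since S0*. Anyone who has started should not be lavaged as a baseline.

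The cost is two urine kits per woman concerned, one short instruction at S0, one reworded line, and an occasional participant lost before B1 or B2. No visit or blood draw is added. A participant lost before B2 also loses her paired lavage value, since the SAP does not impute.

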3.5 Follow-up visits

- i. Visits V1-V3
 - a. **Adverse events form** is completed
 - b. Participant will be given one pill of Vitamin D 50,000 IU and asked to take pill with water at that time
 - c. Complete **vitamin D administration log**
 - d. Schedule next visit in 7 days
 - e. Payment to participant:
- ii. Visit V4
 - a. **Adverse events form** is completed
 - b. Participant will be given one pill of Vitamin D 50,000 IU and asked to take pill with water at that time
 - c. Complete **Vitamin D Subject Specific Accountability Record**
 - d. Schedule next visit in 7 days
 - e. Obtain blood (see **laboratory processing section**)
 - i. One-3.5 ml SST to UNC McLendon Lab for eligibility screening
 - 1. Serum 25OH-Vitamin D
 - 2. Serum Basic metabolic panel
 - f. Confirm contact number to reach participant after 25OH-VitD and BMP resulted.
 - g. Payment to participant:
 - h. Notify study MD when lab results completed

- iii. Visit V5-V7
 - a. **Adverse events form** is completed
 - b. Participant will be given one pill of Vitamin D 50,000 IU and asked to take pill with water at that time
 - c. Complete **Vitamin D Subject Specific Accountability Record**
 - d. Schedule next visit in 7 days
 - e. Payment to participant:

- iv. Visit V8
 - a. **Adverse events form** is completed
 - b. Schedule next visit in 7 days
 - c. Obtain blood (see **laboratory processing section**)
 - i. One 3.5 ml SST to UNC McLendon Lab for eligibility screening
 - 1. Serum 25OH-Vitamin D
 - 2. Serum Basic metabolic panel
 - ii. One 8.5 ml SST for serum storage
 - 1. Serum for 25 OH-Vitamin D and vitamin D binding protein
 - iii. Two 4 ml EDTA Lavender for plasma storage
 - 1. Plasma for cathelicidin
 - d. Confirm contact number to reach participant after 25OH-VitD and BMP resulted.
 - e. Payment to participant:
 - f. Notify study MD when lab results completed
 - a. If vitamin D not >20 ng/ml, participant not eligible for bronchoscopy and will have completed study
 - b. If vitamin D >=20 ng/ml, study staff contact person to arrange bronchoscopy

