- Provide participant one pill of 50,000 IU vitamin D to take with water at visit
- Complete Vitamin D Subject Specific Accountability Record
- Schedule V2 in 7±1 days
- Payment to participant:

Assigned ID: VitD _____	Participant Initials: _____	Date: _____
-------------------------	-----------------------------	-------------

V2- Follow-up visit checklist

- Go to pharmacy
- Complete adverse events form
- Provide participant one pill of 50,000 IU vitamin D to take with water at visit
- Complete Vitamin D Subject Specific Accountability Record
- Schedule V3 in 7±1 days
- Payment to participant:

Assigned ID: VitD _____	Participant Initials: _____	Date: _____
-------------------------	-----------------------------	-------------

V3- Follow-up visit checklist

- Go to pharmacy
- Complete adverse events form
- Provide participant one pill of 50,000 IU vitamin D to take with water at visit
- Complete Vitamin D Subject Specific Accountability Record
- Schedule V4 in 7±1 days
- Payment to participant:

Assigned ID: VitD _____	Participant Initials: _____	Date: _____
-------------------------	-----------------------------	-------------

V4- Follow-up visit with lab draw checklist

- Go to pharmacy
- Complete adverse events form
- Obtain blood testing
 - One-3.5 ml SST to UNC McLendon Lab for eligibility screening
(BMP, 25-OH vitamin D)
- Provide participant one pill of 50,000 IU vitamin D to take with water at visit
- Complete Vitamin D Subject Specific Accountability Record
- Schedule V5 in 7±1 days
- Payment to participant:

Assigned ID: VitD _____

Participant Initials: _____

Date: _____

V5- Follow-up visit checklist

- Go to pharmacy
- Complete adverse events form
- Provide participant one pill of 50,000 IU vitamin D to take with water at visit
- Complete Vitamin D Subject Specific Accountability Record
- Schedule V6 in 7±1 days
- Payment to participant:

Assigned ID: VitD _____	Participant Initials: _____	Date: _____
-------------------------	-----------------------------	-------------

V6- Follow-up visit checklist

- Go to pharmacy
- Complete adverse events form
- Provide participant one pill of 50,000 IU vitamin D to take with water at visit
- Complete Vitamin D Subject Specific Accountability Record
- Schedule V7 in 7±1 days
- Payment to participant:

Assigned ID: VitD _____

Participant Initials: _____

Date: _____

V7- Follow-up visit checklist

- Go to pharmacy
- Complete adverse events form

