- Provide participant one pill of 50,000 IU vitamin D to take with water at visit
- Complete Vitamin D Subject Specific Accountability Record
- Schedule V8 in 7±1 days
- Payment to participant:

Assigned ID: VitD _____	Participant Initials: _____	Date: _____
-------------------------	-----------------------------	-------------

V8- Follow-up visit with lab draw checklist

- Complete adverse events form
- Obtain blood testing
 - One 3.5 ml SST to UNC McLendon Lab for eligibility screening
(BMP, 25-OH vitamin D)
 - One 8.5 ml SST for serum storage (25-OH vitamin D, vitamin D binding protein)
 - Two 4 ml EDTA lavender tube for plasma storage (cathelicidin)
- Provide participant with “Bronchoscopy Handout”
- Confirm contact phone number
- Review labs to determine vitamin D level
 - If 25-OH-VitD \geq 20 mg/ml: Notify MD to schedule bronchoscopy
 - If 25-OH-VitD $<$ 20 mg/ml: Participant not eligible for bronchoscopy; study is completed
 - Bronchoscopy scheduling: Target 1 week \pm 5 days
- Payment to participant:

Assigned ID: VitD _____	Participant Initials: _____	Date: _____
-------------------------	-----------------------------	-------------

B2- Bronchoscopy #2 Visit Checklist

- Review consent form for completion
- Obtain blood testing
 - Two 10 ml Green Top Lithium tubes for PBMC storage
- Review labs to confirm vitamin D ≥ 20 ng/ml
- Escort patient to bronchoscopy
- Payment to participant:
- MD to complete bronchoscopy form
- Staff to complete bronchoscopy sample processing form

SECTION 7: LABORATORY PROCEDURES

1. Plasma processing for cathelicidin

1. Collect two 4 ml EDTA lavender top for plasma, invert 6-12 times after collection
2. Place sample on ice after collection
3. Centrifuge lavender top at 4°C at 1500rpm for 15 minutes.
4. Remove vacutainer tube from the centrifuge, carefully, protecting the layer and not mixing.
5. Remove stopper from the vacutainer tube.
6. Remove plasma and transfer to fresh polypropylene tube. Be careful to not disturb white cells in the buffy coat.
7. Recentrifuge the transferred plasma in order to avoid every contamination with white blood cells: 1500xg at 4°C for 15 minutes
8. Aliquot into 250 microliter aliquots in polypropylene tubes labeled “plasma” (see table below) with study ID
 - a. Individual labels should also include study ID (VitDXXX) and date
9. Storage store at -80°C in polypropylene tubes.

2. Serum processing for 25-OH vitamin D and vitamin D binding protein

1. Collect one 8.5 ml SST for serum.

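### The V4 and V8 checklists in Section 5 omit, or make conditional on vitamin D, the physician notification of laboratory results that Section 3.5 requires at both sites

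*Protocol*

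**What the plan says.** The UNC protocol (version 1.2) and the SPIROMICS/Bayview protocol (version 1.7) read alike on this point.

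Section 1.4 gives the V4 draw a safety purpose: all patients are to "have blood work obtained for calcium level to monitor for hypercalcemia". For V8 it adds "Blood for BMP/ calcium level will also be collected".

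Section 3.5 then says "Notify study MD when lab results completed", once at V4 (item h) and once at V8 (item f). At V8 this instruction stands above the two vitamin D outcomes listed beneath it. Section 3.5 also has staff confirm a contact number at V4 (item f).

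Section 5 presents each visit page as a "checklist of items that must be completed at each visit" and adds "These pages should be printed and used as a step-by-step guide of each visit". The page titled "V4- Follow-up visit with lab draw checklist" covers the adverse events form, the blood draw, the pill, the accountability record, booking V5 and payment; the UNC page opens with a pharmacy trip. The V8 page directs a review of laboratory results for vitamin D only. At or above 20 the next step is "Notify MD to schedule bronchoscopy". Below 20 it is "Participant not eligible for bronchoscopy; study is completed".

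**The concern.** Hypercalcaemia is the drug risk that Section 1.4 singles out for monitoring. A calcium result is useful only if it reaches someone who can judge it. Section 3.5 provides that step. The page in the coordinator's hand leaves it out at V4. At V8 that page applies a different rule: the physician hears only about participants who qualify for the second bronchoscopy, and then for scheduling.

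Two situations matter. At V4, dosing continues at V5, V6 and V7, and the next scheduled calcium is at V8. At V8, a participant below the vitamin D cut-off has finished the study, so no later study visit would pick up an overlooked result.

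**Working it through.** The plan gives no figure to reproduce. The check is a line-by-line comparison of Section 3.5 with the Section 5 checklists, followed by a search of the rest of the documents for other routes.

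**Section 3.5 against Section 5 (same result at both sites)**

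| Step | Section 3.5 | Section 5 checklist |
|---|---|---|
| V4: BMP drawn | Yes (item e) | Yes |
| V4: contact number confirmed | Yes (item f) | Absent |
| V4: study MD notified of results | Yes (item h) | Absent |
| V8: BMP drawn | Yes (item c) | Yes |
| V8: contact number confirmed | Yes (item d) | Yes |
| V8: study MD notified, vitamin D at or above 20 | Yes (item f, before the split) | Yes, but to schedule bronchoscopy |
| V8: study MD notified, vitamin D below 20 | Yes (item f, before the split) | Absent; participant has completed |
| V8: which result is reviewed | Laboratory results generally | Vitamin D only |

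The checklists do carry such lines elsewhere. The S0 checklist has the MD told of blood results, and the S0 and V8 checklists confirm the contact number. The format therefore has room for the V4 items.

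**What lies downstream**

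- Section 1.4 and the visit procedures place doses at V0 to V7, which is 8 doses.
- Doses given at visits after the V4 draw: V5, V6 and V7, so 3 of 8. The V4 pill is also given before its result is known, but that is so under Section 3.5 as well and is not part of the discrepancy.
- Time to the next calcium test: week 8 − week 4 = 4 weeks.

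**How many participants the gap covers**

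- V4: every participant who reaches the visit, up to the target of 20 per site.
- V8: those below 20 ng/ml. The documents do not give this share. If it were 5%, 0.05 × 20 = 1 per site; if 25%, 0.25 × 20 = 5 per site. Both percentages are assumptions for scale only.

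These counts show how many people the checklist gap covers. They do not estimate how many raised calcium results would be missed.

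**Other routes to a physician**

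- Section 4 allows an abnormal laboratory value to count as an adverse finding. Once an adverse event is recognised, the coordinator informs the investigators and staff arrange for a medical provider to see the participant.
- Section 1.4 has weekly screening for hypercalcaemia symptoms and an evaluation at V4. Section 4 has the PI review safety monthly.
- The SAP takes precedence only on endpoints and analyses, and does not mention calcium.

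**Two nearby details**

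UNC describes the V4 and V8 tube as serving eligibility, whereas Section 3.5 at SPIROMICS/Bayview describes it as serving safety. Both V8 checklists print the cut-off in mg/ml, while the rest of the text uses ng/ml. I treat that as a typing error, and nothing here depends on it.

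**The case against.** The strongest reply is that Section 3.5 already gives the order, at both visits and for everyone, under a heading that promises the detailed procedures. Nothing gives Section 5 precedence over it. At V4 the checklist is silent; it does not countermand anything. The gap matters only if staff rely on the checklist and do not go back to Section 3.5. This stands, and it rules out three stronger readings.

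- A reader might infer that a raised calcium would reach nobody. The documents do not support that. Section 3.5 directs notification, and the Section 4 adverse event procedure is a second route. The second route is weaker: the adverse events form is a same-visit item, before results return, and no on-treatment calcium value is defined as abnormal. It exists all the same.
- A reader might infer that the V5 to V7 and B2 checklists also drop a calcium check. They do not. Sections 3.5 and 3.6 contain no such check before those steps, so there is nothing to be inconsistent with.
- A reader might infer that dispensing at V5, or study completion at V8, should wait for calcium review. Neither section says so. That would be a new clinical rule and goes beyond reconciliation.

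It can also be said that the S0 notification line serves scheduling as well as review, so it does not prove that the V4 omission was an oversight. That is fair; the comparison shows only that the format can carry the step.

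The reply does not remove the mismatch. Section 5 calls its items mandatory and its pages the step-by-step guide, and at V8 it states a condition that Section 3.5 does not contain.

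**Conclusion.** The conflict is real and appears in both supplied protocols. Staff who work only from the printed pages are not directed to send the V4 calcium result, or the V8 result when vitamin D is below 20, to a physician. These are the only calcium tests scheduled after dosing begins, and three of eight doses follow the first of them. It is a documentation conflict on a safety step, worth correcting because the correction is so small. It is not evidence that any result went unseen.

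The conclusion rests on three conditions:

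- It describes the versions supplied. The SAP cites a COPD protocol dated 8/23/17, whereas the SPIROMICS/Bayview text here is dated April 20 2016, so that site's wording may since have changed.
- The Section 6 study forms are not in the supplied text. One of them may carry the notification step. The checklists would still differ from Section 3.5.
- The practical effect depends on whether staff use the checklist alone, which the documents cannot show.

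Separately, neither Section 3.5 nor Section 5 links a calcium value to any action at V4 or V8. The only calcium figure, 10.5 mg/dl, is an entry criterion. That is for the investigators to settle.

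**What to change.** Reconcile Section 5 with Section 3.5 at both sites.

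- **V4 checklist:** add the two items that Section 3.5 already lists for that visit, confirming the contact number (item f) and notifying the study MD when results are back (item h).
- **V8 checklist:** place the MD notification of laboratory results above the vitamin D split, as in Section 3.5 item f, so that it applies in both branches. Reconcile the mg/ml and ng/ml units on the same lines.
- Check the current COPD-site protocol and the Section 6 forms, and align them if they differ.

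No calcium threshold, dosing hold or completion rule is proposed. The cost is a few checklist lines in a minor amendment, with no new test, visit or staff.
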